## **6.5 Concomitant Therapy**

### **6.5.1 Acceptable Concomitant Medication**

All treatments that the investigator considers necessary for a participant's welfare may be administered at the discretion of the investigator in keeping with the community standards of medical care except for those that are prohibited as described in Section 6.5.2. All concomitant medication will be recorded on the case report form (CRF) including all prescription, over-the-counter (OTC), herbal supplements, and IV medications and fluids. If changes occur during the study period, documentation of drug dosage, frequency, route, and date may also be included on the CRF.

All concomitant medications received within 30 days before the first dose of study intervention and 30 days after the last dose of study intervention should be recorded. Concomitant medications administered after 30 days after the last dose of study intervention should be recorded for SAEs and ECIs as defined in Section 8.4.

### **6.5.2 Prohibited Concomitant Medications**

Medications or vaccinations specifically prohibited in the exclusion criteria are not allowed during time periods specified by this protocol for that medication or vaccination. If there is a clinical indication for any medications or vaccinations specifically prohibited, discontinuation from study intervention may be required. The investigator should discuss any questions regarding this with the Sponsor Clinical Director. The final decision on any supportive therapy or vaccination rests with the investigator and/or the participant's primary physician. However, the decision to continue the participant on study intervention requires the mutual agreement of the investigator, the Sponsor, and the participant.

Participants are prohibited from receiving the following therapies during the Screening and study intervention phase(s):

1. Antineoplastic systemic chemotherapy or biological therapy
2. Immunotherapy not specified in this protocol
3. Chemotherapy not specified in this protocol
4. Investigational agents other than MK-8353 and selumetinib
5. Any supplemental vitamin E. High doses of vitamin E have been reported to cause bleeding and interrupt blood coagulation processes.
  - Selumetinib capsules contain vitamin E in the form of D- $\alpha$ -tocopheryl polyethylene glycol 1000 succinate (TPGS), a water-soluble form of vitamin E, which acts as a formulation excipient.
  - Selumetinib should be administered with caution in participants who are receiving concomitant coumarin anticoagulant medications, eg, warfarin. These participants should have their INR monitored, anticoagulant assessments conducted more frequently, and the dose of the anticoagulant therapy adjusted accordingly.
6. Radiation therapy
7. Agents that may affect the metabolism of MK-8353 or selumetinib (eg, strong/moderate inhibitors or inducers of CYP3A4 and CYP2C19), unless considered clinically indicated ([Table 5](#))

Note: Radiation therapy to a symptomatic solitary lesion or to the brain may be allowed at the investigator's discretion after the DLT observation period in order for the participant to be considered evaluable for DLT.

Note: If the PI determines the use of such agent is clinically indicated, caution must be taken when co-administering these agents with MK-8353 and selumetinib.

8. Compounds with a narrow therapeutic index that are substrates for CYP3A4, -2C8, OATP1B1/3, and OCT2 should be avoided (Table 5). Once study treatment is initiated, the participant must not take medications listed in Table 5 during the course of the study.
- Table 5 is not a comprehensive listing. The investigator must use his/her medical judgment when a participant presents with a medication not on the list or call the Sponsor for clarification as needed. The investigator should consult an actively updated list of drugs that are clinically relevant inducers, or inhibitors of CYP450, including CYP2C19 and CYP3A4, and a narrow therapeutic index that are substrates for CYP3A4, -2C8, OATP1B1/3, and OCT2, as well as the product labeling of these compounds for reference.

Table 5 Examples of CYP3A4 Inducers/Inhibitors and Narrow Therapeutic Index Substrates of CYP3A4, CYP2C8, OATP1B1/3 and OCT2 Prohibited During the Trial

Strong CYP3A4 Inhibitorsa,g	Strong CYP3A4 Inducersb,g	Moderate CYP3A4 Inhibitorsc,g	Moderate CYP3A4 Inducersd,g
Atazanavir Cannabis (oral, IV) Clarithromycin Cobicistat Conivaptan Danoprevir and ritonavir Dasabuvir Elvitegravir and ritonavir Grapefruit juice and other juices f Idelalisib Indinavir and ritonavir Itraconazole Ketoconazole Lopinavir and ritonavir Paritaprevir and ritonavir (ombitasvir and/or dasabuvir) Posaconazole Nefazodone Nelfinavir Ritonavir Saquinavir and ritonavir Telithromycin Tipranavir and ritonavir Troleandomycin Voriconazole	Carbamazepine Enzalutamide Mitotane Phenobarbital Phenytoin Rifabutin Rifampin St John's wort e	Amprenavir Aprepitant Cimetidine Ciprofloxacin Clotrimazole Crizotinib Cyclosporine Diltiazem Dronedarone Erythromycin Fluconazole Fluvoxamine Fosamprenavir Imatinib Tofisopam Verapamil Grapefruit juice and other juices f	Bosentan Efavirenz Etravirine Modafinil
CYP3A4 Substrates with Narrow Therapeutic Index h	CYP2C8 Substrates with Narrow Therapeutic Index h	OATP1B1/1B3 Substrates with Narrow Therapeutic Index i	OCT2 Substrates with Narrow Therapeutic Index i
Alfentanil Alprazolam Astemizole Cisapride Ergotamine Diergotamine Cyclosporine Fentanyl (including Duragesic) Hydrocodone Lovastatin Lurasidone Paclitaxel Pimozide Quinidine Rivaroxaban Sirolimus Tacrolimus	Cisapride Repaglinide Paclitaxel	Asunaprevir Atorvastatin Bosentan Danoprevir Docetaxel Glyburide Nateglinide Paclitaxel Pitavastatin Pravastatin Rosuvastatin Simvastatin	Dofetilide Metformin

Strong CYP3A4 Inhibitors a,g	Strong CYP3A4 Inducers b,g	Moderate CYP3A4 Inhibitors c,g	Moderate CYP3A4 Inducers d,g

CYP = cytochrome P450; OATP = Organic Anion Transporting Polypeptide; OCT = Organic Cation Transporter
 
a Strong inhibitors are drugs that increase the plasma AUC of sensitive CYP index substrates by <math>\geq 5</math>-fold.
 
b Strong inducers are drugs that decrease the plasma AUC of sensitive CYP index substrates by <math>\geq 80\%</math>.
 
c Moderate inhibitors are defined as causing a <math>\geq 2</math>- but <math>< 5</math>-fold increase in the AUC values of sensitive CYP index substrates when the inhibitors were given at the highest approved dose and the shortest dosing interval in clinical evaluations.
 
d A moderate inducer decreases the AUC of a sensitive index CYP substrate by <math>\geq 50\%</math> to <math>80\%</math>.
 
e The effect of St John's wort varies widely and is preparation-dependent.
 
f The effect of grapefruit juice varies widely among brands and is concentration-, dose-, and preparation-dependent. Studies have shown that it can be classified as a "strong CYP3A inhibitor" when a certain preparation was used (eg, high dose, double strength) or as a "moderate CYP3A inhibitor" when another preparation was used (eg, low dose, single strength).
 
g Compiled from the table of substrates, inhibitors and inducers available at:  https://www.fda.gov/Drugs/DevelopmentApprovalProcess/DevelopmentResources/DrugInteractionsLabeling/ucm093664.htm ("Drug Development and Drug Interactions: Table of Substrates, Inhibitors and Inducers").
 
h CYP3A4 and CYP2C8 substrates with narrow therapeutic range refers to drugs whose exposure-response indicates that increases in their exposure levels by the concomitant use of CYP3A4 or CYP2C8 inhibitors may lead to serious safety concerns. For specific information, refer to the Classification of Substrates tables, accessible at the following link:  https://www.fda.gov/drugs/developmentapprovalprocess/developmentresources/druginteractionslabeling/ucm093664.htm (In subsection "CYP Enzymes", select "Clinical substrates").
 
i OATP1B1/1B3 and OCT2 substrates with narrow therapeutic range refers to drugs whose exposure-response indicates that increases in their exposure levels by the concomitant use of OATP1B1/1B3 or OCT2 inhibitors may lead to serious safety concerns. For specific information, refer to the Classification of Substrates tables, accessible at the following link:  https://www.fda.gov/drugs/developmentapprovalprocess/developmentresources/druginteractionslabeling/ucm093664.htm (In subsection "Transporters", select "Clinical substrates").
			

Based on investigator assessment, participants who require the use of any of the aforementioned treatments for clinical management should be discontinued from study intervention and continue in the Post-treatment Follow-up Phase as outlined in the SoA (Section 1.3). Participants may receive other medications that the investigator deems to be medically necessary.

### 6.5.3 Supportive Care

#### 6.5.3.1 MK-8353 Supportive Care

Medications required to treat AEs or concurrent illnesses other than those prohibited in Section 6.5.2 are allowed during the study. These include antiemetics, growth factors, and other supportive care medications. Contraceptive medications as described in Appendix 5 are allowed.

Bisphosphonates are allowed for subjects with lytic bone metastases. Antiemetics, including serotonin-receptor antagonists, metoclopramide, prochlorperazine, or thiethylperazine are allowed. Aprepitant is a CYP3A4 inhibitor and should not be used in the study.

Skin rash has been observed in subjects treated with inhibitors of the MAPK pathway and is expected in the current study. It may be representative of an on-target effect of the study medication. Appropriate clinical management of skin rash may be utilized as clinically indicated. An algorithm based on dermatology best practices for other contemporary targeted agents that cause skin toxicity is offered below as guidance to manage skin toxicities seen in subjects being treated on this protocol. The algorithm suggests a step-wise approach to rash management.

- If the rash is NCI CTCAE Grade 1, consider starting with topical steroids (eg, betamethasone), topical antibiotics such as clindamycin gel, or no treatment if the subject is asymptomatic. Use of topical steroid cream with higher potency may be considered early in subjects with moderate rash on the face.
- If the rash is NCI CTCAE Grade 2, continue topical steroid or pimecrolimus cream and consider adding an oral tetracycline or a similar agent.
- If the rash reaches NCI CTCAE Grade 3 or above, dose interruption and/or dose reduction, coupled with the addition of topical steroids is recommended.
- Pruritus of any grade may be treated with an antihistamine, such as diphenhydramine or hydroxyzine hydrochloride.
- Xerosis can be treated with classical emollients.
- Secondary infection may complicate or worsen skin toxicity. To reduce the likelihood of nasal infection, intranasal mupirocin may be considered. Infected rash may be treated with a short course of an oral tetracycline, such as doxycycline. Sun exposure should be avoided in subjects receiving doxycycline or other tetracycline antibiotics.
- If there is a clinical diagnosis of impetigo, or an infection with *Staphylococcus aureus* is confirmed, topical mupirocin may be used. Infected lesions suspected to be treatment-resistant should be cultured. If there is no improvement after 2 weeks of treatment, therapy for the rash should be considered ineffective and discontinued.
- Additionally, oral antihistamines (nonsedative) may also be considered for the treatment of Grade 1 to 3 rashes. Oral steroids may be considered for Grade 3 rash.

Every medication taken by the subject during the trial and the reason for use must be recorded in the electronic case report form (eCRF). Note that the use of any concomitant medication must relate to the documented medical history, prophylaxis, or an AE of the subject.

Subjects will be permitted to receive appropriate supportive care measures as deemed necessary by the treating physician including but not limited to the items outlined below:

- **Diarrhea:** diarrhea should be treated promptly with appropriate supportive care, including loperamide. Subjects should be instructed to begin taking loperamide at the first sign of: 1) poorly formed or loose stool, 2) occurrence of more bowel movements than usual in one day, or 3) unusually high volume of stool. Loperamide should be taken in the following manner: 4 mg at first onset of diarrhea, then 2 mg after each unformed stool. The daily dose of loperamide should not exceed 16 mg/day. Loperamide should be deferred if blood or mucus is present in the stool or if diarrhea is accompanied by fever. In this setting, appropriate diagnostic microbiologic specimens should be obtained to exclude an infectious etiology. Subjects should be also advised to drink liberal quantities of clear fluids to help prevent dehydration. Supportive care according to institutional guidelines in the context of standard of care for diarrhea are permitted (except prohibited medications; see Section 6.5.2).
- **Nausea/vomiting:** nausea and vomiting should be treated aggressively. After an initial occurrence of Grade 2 or higher nausea or vomiting, strong consideration should be given to the administration of prophylactic antiemetic therapy according to standard institutional practice. Subjects should be strongly encouraged to maintain liberal oral fluid intake.
- **Anemia:** transfusions and/or erythropoietin may be utilized as clinically indicated per American Society of Clinical Oncology (ASCO)/American Society of Hematology (ASH) guidelines after the first cycle of combination therapy for the treatment of anemia, but should be clearly noted as concurrent medications.
- **Neutropenia:** colony-stimulating factors including G-CSF, pegylated G-CSF or GM-CSF according to ASCO/ASH guidelines after the first cycle of combination therapy. Colony-stimulating factors can be administered for the management of neutropenia toxicities after Cycle 1.
- **Thrombocytopenia:** transfusion of platelets may be used per ASCO/ASH guidelines if clinically indicated.
- **Anti-infectives:** subjects with a documented infectious complication should receive oral or IV antibiotics or other anti-infective agents as considered appropriate by the treating investigator for a given infectious condition, according to standard institutional practice.

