**For complicated Grade 1/2 diarrhea or any Grade 3 to 4 diarrhea**

- The participant must call the investigator immediately
- If loperamide has not been initiated, initiate loperamide immediately. Initial administration 4 mg, then 2 mg every 4 hours (maximum of 16 mg/day) or after each unformed stool.
- Administer IV fluids and electrolytes as needed. In case of severe dehydration, replace loperamide by octreotide.
- Monitor/continue IV fluids and antibiotics as needed. Intervention should be continued until the participant is diarrhea free for at least 24 hours.
- Hospitalization may need to be considered.

**Skin Toxicity:** Clinical judgment and experience of the treating physician should guide the management plan of each participant. In general, the following interventions are in addition to the rash dosing adjustment guidelines in [Table 6](#).

- Prophylaxis of skin toxicity to be initiated 24 hours prior to the first treatment with study drug or later as needed.

- Application of topical agents to the most commonly affected skin areas such as face, scalp, neck, upper chest and upper back.

Topical agents include non-oily sunscreen (para-aminobenzoic acid [PABA] free, SPF  $\geq 30$ , ultraviolet A [UVA]/ultraviolet B [UVB] protection), topical steroids (preferably mometasone cream ie, Elocon®) and topical erythromycin (ie, Eryaknen® or topical pimecrolimus).

**Note:** Topical agents should be applied on a daily basis starting on Day 1 of study treatment or 24 hours prior to the first dose, and more often as needed.

- Possibly oral doxycycline (100 mg daily) for the first 2-3 weeks of study drug administration.

Other effective medications are antihistamines, other topical corticosteroids, other topical antibiotics and low-dose systemic corticosteroids.

The treatment algorithm based on CTCAE grade is as follows:

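### Loperamide for severe or complicated diarrhea with blood, mucus or fever: 6.5.3.1 says defer, 6.5.3.2 says start at once, and nothing says which prevails

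*Combined protocol and SAP*

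**What the plan says.** The Synopsis (1.1, Intervention Groups and Duration) describes a single intervention group receiving both drugs, and 6.6.3.1 has them taken together. The supportive-care text is nevertheless written drug by drug.

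- **6.5.3.1, diarrhea item.** Treat promptly, with loperamide from the first loose stool. It then sets a limit: "Loperamide should be deferred if blood or mucus is present in the stool or if diarrhea is accompanied by fever". In that setting, "appropriate diagnostic microbiologic specimens should be obtained to exclude an infectious etiology". The limit is not tied to any grade. The item ends by allowing other care: "Supportive care according to institutional guidelines in the context of standard of care for diarrhea are permitted", prohibited medications excepted.
- **6.5.3.2, complicated Grade 1/2 or any Grade 3 to 4 diarrhea.** The list opens with "The participant must call the investigator immediately". The next bullet is "If loperamide has not been initiated, initiate loperamide immediately", with the dose "Initial administration 4 mg, then 2 mg every 4 hours (maximum of 16 mg/day) or after each unformed stool". The one stated departure is "In case of severe dehydration, replace loperamide by octreotide". The list also covers IV fluids, antibiotics as needed and possible hospitalization.
- **6.5.2.** "The final decision on any supportive therapy or vaccination rests with the investigator and/or the participant's primary physician".

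**The concern.** The 6.5.3.1 deferral is a precaution against giving an antimotility drug while infection is still possible; the section states that purpose itself when it asks for specimens. The 6.5.3.2 diarrhea guidance never mentions blood, mucus or fever and does not refer back to 6.5.3.1. A site that opens the selumetinib section for a febrile participant with Grade 3 diarrhea, and does as it says, gives loperamide in the situation where the MK-8353 section withholds it.

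The overlap arises naturally. A participant who correctly held off loperamide because of fever or bloody stool is exactly someone in whom it has not been started. If the diarrhea then reaches Grade 3 or 4, the 6.5.3.2 bullet applies and reverses the precaution. Diarrhea is also anticipated: both drugs have dedicated guidance for it, and Table 7 gives it its own rows.

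What is at stake is participant safety and consistent practice across sites.

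**Working it through.** The point is textual, so the check sets the two rules side by side, looks for any text that ranks them, and then sizes the difference in dose. The plan has no figure of its own to reproduce here.

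**1. The two rules by situation, loperamide not yet started**

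| Situation | 6.5.3.1 | 6.5.3.2 | Conflict? |
|---|---|---|---|
| Uncomplicated Grade 1/2 with blood, mucus or fever | Defer | Consider loperamide | No: 6.5.3.2 only invites consideration |
| Complicated Grade 1/2 with blood, mucus or fever | Defer | Start immediately | Yes |
| Any Grade 3 to 4 with blood, mucus or fever | Defer | Start immediately | Yes |
| Complicated Grade 1/2 or Grade 3 to 4 without those features | Start at first sign | Start immediately | No |

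The protocol does not define complicated diarrhea. The conflict does not depend on that term, because the Grade 3 to 4 row stands without it. The conflict concerns loperamide timing only: 6.5.3.2 is silent on microbiologic specimens, and silence does not contradict the request for them in 6.5.3.1.

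**2. Does any text rank the two sections?**

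- The tie-break for conflicting recommendations in 6.6.4.1 covers adjustment of study-drug dose, not supportive medication.
- The Table 7 diarrhea rows cover interruption and reduction of study drug only.
- The final-decision sentence in 6.5.2, the discretion wording in 6.5.1, and the lead-in to the 6.5.3.1 list all say who decides.
- The institutional-guideline sentence in 6.5.3.1 permits other care without ordering the two rules.
- The call to the investigator in 6.5.3.2 puts a physician in the loop, but the very next bullet tells that physician to start loperamide.

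None of these states which loperamide rule applies.

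**3. Size of the difference between the rules**

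Inputs from the 6.5.3.2 list: 4 mg at the start, then 2 mg every 4 hours, maximum 16 mg/day. Within the first 24 hours the repeat doses fall at hours 4, 8, 12, 16 and 20, which is 5 doses:

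4 + 5 × 2 = 14 mg.

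The alternative of dosing after each unformed stool is limited by the 16 mg/day maximum. Under 6.5.3.1 the amount is 0 mg for as long as loperamide is deferred. This expresses the choice between giving and deferring as a dose; it is not an estimate of harm. The documents give no rate for the situation, so no expected number of participants is calculated.

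**The case against.** The strongest reply is that the texts can be read together. The 6.5.3.1 item itself pairs an urgent start rule with an exception for blood, mucus or fever, and that exception has no grade limit. On a specific-over-general reading, a site would start loperamide at once under 6.5.3.2 unless those features were present, and so honour both sections. Supportive care is also discretionary throughout: 6.5.1, 6.5.2 and the lead-in to the 6.5.3.1 list place the decision with the treating physician. On that view only a cross-reference is missing.

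The reading is sensible, and the fix adopts it. But the protocol does not state it, and the opposite is also open: 6.5.3.2 is itself specific, to more severe diarrhea, and names its own single departure, so a site could take it as controlling. Discretion identifies the decision-maker and leaves two contrary instructions in front of that person.

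Other parts of the reply do stand. Section 6.5.3.1 does not say when the deferral ends, so it cannot be read as lasting only until specimens are taken. The affected group is narrow, and narrower still because both sections push for early loperamide. The IV fluids, antibiotics and possible hospitalization in 6.5.3.2, and the anti-infectives for documented infection in 6.5.3.1, limit the harm. The participant loperamide instructions mentioned in 6.5.3.2 are not in the documents, so no gap in them is shown; they may already carry the deferral.

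**Conclusion.** The concern holds. For complicated Grade 1/2 or any Grade 3 to 4 diarrhea with blood, mucus or fever, before loperamide has been started, the protocol gives opposite written instructions and no rule for choosing between them. The sponsor should correct this in the next amendment: followed as written, 6.5.3.2 overrides the sponsor's own precaution. The difference in treatment is 14 mg in the first 24 hours on the four-hourly schedule against none while deferred.

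The conclusion rests on both sections applying to every participant, which the single combination group establishes, and on the absence of any precedence text. It does not rest on an event rate or on the content of the participant instructions. No effect on dose-limiting toxicity classification, escalation decisions or endpoints is claimed.

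**What to change.** In 6.5.3.2, under complicated Grade 1/2 or any Grade 3 to 4 diarrhea, extend the bullet "If loperamide has not been initiated, initiate loperamide immediately" with an exception along these lines: *unless the stool contains blood or mucus or the participant has fever; in that case hold loperamide and take microbiologic specimens as described in 6.5.3.1.* Check that the participant loperamide instructions referred to in 6.5.3.2 carry the same exception, and add it if they do not.

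The cost is one clause in the next amendment and one check of the instructions. The specimens are already called for in 6.5.3.1, so there are no added visits, participants or analyses. Amendment 01 already revised the 6.5.3.1 diarrhea text for clarity and alignment with other sections; this change would extend that alignment to 6.5.3.2.
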